A flow diagram is shown below: Initially, twenty women were recruited to the training via an online advertisement and a local newspaper, but only 19 showed up for pre-testing. After a medical examination, one participant was excluded due to low BMD (T-score < -3 SD), and two were excluded due to high BMI (≥ 30 kg/m²). In addition, one woman refrained from participating in the training, and thus, 15 participants were recruited to MMT. During the study, two participants in MMT dropped out due to personal reasons and at the end of the study four participants were excluded in the analyses as their average attendance to the program was less than one hour per week. CON consisted of 13 age-matched sedentary postmenopausal women (12 from a previous study plus the woman who refrained from participating in the training), and therefore 9 MMT and 13 CON was finally included in the data analyses.

A Feasibility Study of Training in a Local Community Aimed Upon Health Promotion with Special Emphasis on Musculoskeletal Health Effects

CONSORT Flow Diagram

Participants' baseline characteristics, including maximum oxygen consumption (VO₂-max), are shown in Table 1.

Table 1. Baseline characteristics of the participants

	MMT (n=9)	CON (n=13)	p-value
Age (years)	62.4 ± 3.8	58.7 ± 4.7	0.061
Height (cm)	166.9 ± 6.4	166.9 ± 5.2	0.989
Weight (kg)	72.8 ± 5.6	64.2 ± 10	0.022*
BMI (kg/m ²)	26.3 ± 2.2	22.9 ± 2.9	0.009*
Body Fat Percentage (%)	39.4 ± 3.1	33.7 ± 8.5	0.070
Total Fat Mass (kg)	28.7 ± 2.7	22.2 ± 8.6	0.043*
Total Lean Body Mass (kg)	41.8 ± 4.3	39.8 ± 3.4	0.233
VAT-mass (g)	793 ± 351.2	511 ± 434.8	0.123

A Feasibility Study of Training in a Local Community Aimed Upon Health Promotion with Special Emphasis on Musculoskeletal Health Effects

VAT-volume (cm ³)	840.6 ± 372.2	541.7 ± 460.9	0.123
Total BMC (g)	2266.9 ± 206.5	2067.2 ± 300.2	0.100
BMD (g/cm ²)			
Whole-body	1.121 ± 0.073	1.046 ± 0.099	0.066
Lumbar spine	1.088 ± 0.137	1.014 ± 0.111	0.175
Right Femur neck	0.918 ± 0.092	0.834 ± 0.097	0.057
Left Femur neck	0.941 ± 0.088	0.823 ± 0.076	0.003*
Mean Femur neck	0.929 ± 0.089	0.829 ± 0.085	0.015*
Right Total Femur	0.947 ± 0.098	0.864 ± 0.091	0.056
Left Total Femur	0.949 ± 0.101	0.840 ± 0.091	0.016*
Mean Total Femur	0.948 ± 0.098	0.852 ± 0.090	0.028*
Right Trochanter	0.741 ± 0.087	0.683 ± 0.092	0.149
Left Trochanter	0.745 ± 0.091	0.661 ± 0.097	0.055
Mean Trochanter	0.743 ± 0.086	0.672 ± 0.093	0.084
Right Shaft	1.151 ± 0.126	1.046 ± 0.125	0.068

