To test the BMD exclusion criteria at baseline as well as evaluate bone adaptation after 19wk of training, BMD (g/cm^2) of proximal femur (PF), lumbar spine (LS), and whole-body (WB) were assessed by Dual-energy X-ray Absorptiometry scanning (iDXA, Lunar Corporation, Madison, Wisconsin, USA) according to standard procedures. The regions of interest were determined by the encore software (encore software version 14.10.022, GE Medical Systems, Madison, United States). In addition, body composition was evaluated by the whole-body scan: body weight (BW, kg), BMI (kg/m^2), body fat percentage (%BF, %), total fat mass (FM, g), total lean body mass (LBM, g), visceral adipose tissue (VAT) mass (g) and volume (m^3), and total bone mineral content (BMC, g). The participants were asked to remove metal objects and empty their bladder prior to scanning.

Blood sampling & Biochemical analyses

The plasma concentration of BTM at BASE, after 3wk, and after 19wk of training were measured. After an overnight fast and without any vigorous activities in the previous 48 hours, participants showed up in the laboratory in the early morning. Blood samples were collected from the antecubital vein with a butterfly needle, then transferred to EDTA tubes and centrifuged immediately. The plasma fractions were put on dry ice. Eighteen ml of blood were taken from each participant per test day. Following each test, a sample was placed at -80°C for future P1NP, OC, and CTX analysis, which were assessed by the Chemiluminescence method using a fully automated immunoassay system (iSYS, Immunodiagnostic Systems Ltd., Bolton, England). The assay performance expressed as inter-run variation coefficients were 8% for P1NP, 9% for OC, and 10% for CTX.

Training status

To estimate the participants' general training status, a progressive test of maximal oxygen uptake ($\text{VO}_2\text{-max}$) ($\text{ml}/\text{kg}/\text{min}$) was performed on an electronic ergometer cycle (Monark 839E, Monark Exercise AB, Vansbro, Sweden) according to standard procedures. A breath-by-breath gas online analyzing system (Jaeger Oxycon Pro, VIASYS Healthcare, Höchberg, Germany) was connected to the participant, and a direct $\text{VO}_2\text{-max}$ measurement was conducted.

Dynamic balance

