The “four square step test” (FSST) was performed to evaluate the dynamic balance [18] in MMT. The test requires a person to move systematically forward, sideward, backward, and sideward again over four narrow sticks circa 2.5 cm in diameter and 100 cm in length placed on the floor like a cross. The participants were requested to complete the sequence as fast as possible without touching the sticks. The participants started by facing the cross in the lower left quadrant, stepped forward over the stick into the next left quadrant, stepped sideward over the stick again into the upper right quadrant, and stepped backward over the stick into the lower right quadrant, then stepped sideward over the stick into the left quadrant where they started. Thus, they were moving in a clockwise direction. The floor in each square must be contacted by both feet, and the participants were asked to face forward for the whole sequence if possible. The participants were allowed to turn to step into the next square if needed. They started and finished in the same square, and the score were given in seconds (sec). The test was done twice, and the fastest time was used as the FSST score.

Functional muscle strength and power

The functional muscle strength and power were evaluated in MMT by a jump-and-reach test (vertical jump height) (Vertec Sports Imports, Hilliard, OH). First, the participants were taught how to perform a countermovement jump and how to displace the vanes that was placed above reaching height on a vertical stand. After thoroughly instruction and familiarization, the jump-and-reach test was performed. The maximum vertical jump height (cm) was determined by the difference between the participant standing reach height and the highest displaced vane. The greatest value out of three trials was taken as the result.

Statistical analysis

All of the statistical analyses were conducted using the Statistical Package for the Social Sciences (SPSS, version 26.0, IBM Corp., Armonk, NY, USA). The standard descriptive statistics and unpaired T-test were used to describe and test the baseline characteristics of the participants. Repeated measurements ANOVA and general linear model with post hoc tests were used to test the effect of training on BTM, BMD, dynamic balance, and the jump-and-reach test. A p-value < 0.05 was considered significant.

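### At least eight training-effect outcomes are each judged at p < 0.05, with no primary outcome, exploratory label or adjustment across outcomes

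*Combined protocol and SAP*

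**What the plan says.** The Statistical analysis section states that repeated-measures ANOVA and a general linear model with post hoc tests were "used to test the effect of training on BTM, BMD, dynamic balance, and the jump-and-reach test". It then sets a single threshold: "A p-value < 0.05 was considered significant". The post hoc method is not named.

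The measurement sections show what lies behind the four outcome groups:

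- **Bone turnover markers.** Samples were stored "for future P1NP, OC, and CTX analysis", so there are three markers. The timing is given as "The plasma concentration of BTM at BASE, after 3wk, and after 19wk of training were measured", so each has two follow-up values.
- **BMD.** The section BMD and body composition says that "proximal femur (PF), lumbar spine (LS), and whole-body (WB) were assessed", which is three sites. Table 1 splits the femur further. It has 14 BMD rows, 12 of them femoral: right, left and mean for four regions, for example "Mean Femur neck". The plan does not say which of these are tested for a training effect.
- **Balance.** The four square step test (FSST) "was performed to evaluate the dynamic balance [18] in MMT", that is, in the training group only.
- **Jump.** "The functional muscle strength and power were evaluated in MMT by a jump-and-reach test", again without controls.

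The documents name no primary outcome, primary contrast, testing order or correction across outcomes. They call the study a feasibility study, but the Training program section gives its purpose as evaluating the osteogenic impact of the training.

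**The concern.** One threshold applied separately to many outcomes gives many chances of a significant result. The plan does not say in advance which marker, skeletal site or time point would support a claim that the training affects bone, so whichever one crosses 0.05 could be presented as that effect. The feasibility label does not settle this, because the significance rule is not marked as exploratory.

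What is at stake is how a lone p < 0.05 from 9 trained women and 13 controls is read. A reader who takes the rule at face value would credit such a result with a 5% error rate, and that rate does not hold across the set of tests.

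**Working it through.** The plan states no familywise error rate, power or sample size calculation, so there is no figure of its own to reproduce.

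**Inputs from the documents.** Per-test threshold 0.05 (Statistical analysis; sidedness not stated, two-sided assumed). Analysed women: 9 in the training group (MMT) and 13 controls (CON) (Participants and Table 1).

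**Count of outcomes.** 3 markers + 3 BMD sites + FSST + jump = 8. Bone tests that compare the groups: 3 + 3 = 6. If the four mean femur regions of Table 1 replace the single femur site, BMD has 4 + lumbar spine + whole body = 6 sites, giving 9 bone tests and 3 + 6 + 2 = 11 outcomes.

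**Upper end, independent tests.** Chance of at least one false positive = 1 - 0.95^k.

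- k = 6: 1 - 0.95^6 = 0.265
- k = 8: 1 - 0.95^8 = 0.337
- k = 9: 1 - 0.95^9 = 0.370
- k = 11: 1 - 0.95^11 = 0.431

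**Correlated tests.** The correlations of change are assumptions. Normal changes with no true effect were simulated at the actual group sizes (100,000 runs per case). Each bone outcome was tested by a two-sample t test on the 19-week change, t = (mean MMT - mean CON) / [s × √(1/9 + 1/13)] with 20 degrees of freedom. With two time points this equals the group-by-time test of a repeated-measures ANOVA. For the markers it uses 19 weeks only. FSST and jump were tested by a paired t test in the 9 trained women (8 degrees of freedom).

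| Assumed correlation of changes | 6 bone tests | All 8 outcomes |
|---|---|---|
| 0 | 27% | 34% |
| 0.5 within markers and within BMD, 0 elsewhere | 24% | 31% |
| 0.9 within markers and within BMD, 0 elsewhere | 16% | 24% |
| 0.3 throughout | 24% | 31% |
| 0.5 throughout | 21% | 27% |
| 0.7 throughout | 17% | 22% |
| 0.9 throughout | 11% | 15% |

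The simulated 27% in the first row is the exact 26.5% within simulation error. If FSST and jump are also correlated at 0.9 with each other, the 24% in the third row becomes 22%.

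**Range.** All eight: 15-34%, that is 15/5 = 3 to 34/5 ≈ 7 times the nominal 5%. Six bone tests: 11-26%, that is 11/5 ≈ 2 to 26/5 ≈ 5 times.

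**Wider testing.** With the mean femur regions, the range over the same assumptions is 13-37% for the 9 bone tests and about 16-43% for the 11 outcomes. With the original eight outcomes, suppose unadjusted marker contrasts at both 3 and 19 weeks are read at 0.05. With correlations within families of 0.9 down to 0 and independence between families, the chance is then 28-42%, against 22-34% for 19 weeks alone.

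**The case against.** The strongest case on the other side has four parts.

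1. **This is a feasibility study of 22 women, and formal multiplicity control is often not expected there.** This stands, and statisticians would reasonably differ on formal control here. It argues for a label rather than an adjustment. It does not justify an unqualified significance rule.

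2. **The global null fits poorly, and bias matters more than chance.** This also stands. Twelve of the 13 controls came from a previous study. The groups differ at baseline, for example CTX 331.2 against 627.8 ng/l and osteocalcin 19 against 28.9 μg/l. Four women were dropped for low attendance. FSST and jump are before-after tests without controls, in a programme that trains jumping and balance, so no change at all is hard to believe for those two. A reader might infer that 15-34% is the study's real false-positive risk. The documents do not support that, because the calculation assumes comparable groups and no true change.

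3. **The size depends on unknown correlations.** It does. A reader might take only the upper figures and conclude that the error is always at least four times nominal. At a common correlation of 0.9 it is about three times for all eight outcomes and about two times for the six bone tests.

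4. **The post hoc tests may carry a correction.** Since the method is unnamed, some adjustment across time points cannot be excluded. It would act within one model and would not cover separate outcomes.

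**Conclusion.** The point holds as a matter of labelling. The plan calls any of at least eight training-effect results significant at 0.05 without a primary outcome, an exploratory label or an adjustment across outcomes. Under no true effect, two-sided tests, normal changes and assumed correlations from 0 to 0.9, the chance of at least one false positive is about 15-34% for all eight and about 11-26% for the six bone tests. The second range is the relevant one for a claim about bone, since FSST and jump cannot be presented as an osteogenic effect. Both rise if more femur regions or both marker follow-ups are tested.

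A reader might go further and infer that formal control is required, or that a significant result from this study must be a chance finding. Neither follows. The documents describe a feasibility study, written in the past tense and with final analysis numbers, and the calculation isolates multiplicity from the design's other problems. This is a cheap improvement, not a defect that decides whether the analysis can be used.

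**What to change.** For training effects, replace the threshold sentence in the Statistical analysis section with:

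*All training-effect results are exploratory; each is reported as an estimate with 95% CI and no confirmatory significance claim, and every outcome, time point and femur region tested is listed.*

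Add that this limits the over-reading of chance findings only, and does not remove bias from the non-randomised comparison.

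The cost is wording; no new data are needed. The downside is that no result then carries a confirmatory significance claim.

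Naming one primary outcome and one contrast is an option only if outcome data are still unseen. The documents do not show whether follow-up results had been seen, but final analysis numbers and completed attendance exclusions make that route unlikely to apply. A primary outcome chosen after seeing results would not cure the problem.
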